### 14.2 Trial analysis sets

All screened subjects will be accounted for in the CTR.

All subjects randomised and exposed to IMP will be included in the full analysis set (FAS) and will be analysed for efficacy. Exclusions from the FAS can be considered in special cases as described in ICH E9, Section 5.2.1., Full Analysis Set. If it is decided to exclude a subject from the FAS, a justification addressing ICH E9 will be given.

A safety analysis set (SAF) will be defined as all subjects who will be exposed to IMP.

A PK analysis set will be defined as all subjects who will be exposed to LEO 138559 and provide samples for measuring serum concentrations of LEO 138559.

The decisions regarding inclusion/exclusion of subjects or subject data from the trial analysis sets will be documented in the analysis set definition document before breaking the randomisation code.

THIS DOCUMENT CONTAINS CONFIDENTIAL INFORMATION AND MUST NOT BE COPIED OR MADE AVAILABLE TO ANY THIRD PARTY WITHOUT THE PRIOR WRITTEN CONSENT OF THE LEO PHARMA GROUP

## 14.3 Statistical analysis

### 14.3.1 General principles

All significance tests will be two-sided using the 5% significance level. All confidence intervals will be presented with 95% degree of confidence, unless otherwise specified. Efficacy analyses will be based on the FAS, and safety analyses will be based on the safety analysis set. PK analysis will be based on the PK analysis set.

If not mentioned otherwise, endpoints will be summarised descriptively at each visit by treatment. For endpoints evaluated over time, plots will be made to explore the trajectories with time.

An observed cases approach will be used for tabulations of data by visit (that is, involving only those subjects who attended each specific visit). For categorical endpoints, the number of subjects not attending each specific visit will also be provided.

Categorical data will be summarised by treatment group, using the number and percentage of subjects in each category. Continuous data will be summarised using the mean, median, standard deviation (SD), 1st quartile, 3rd quartile, minimum, and maximum values.

Additionally, geometric mean and coefficient of variation (CV) will be provided for the PK endpoint.

In general, for endpoints evaluated as change from baseline and/or where a baseline adjustment is applied, baseline is defined as assessments conducted at the randomisation visit (Visit 3), if not otherwise stated. If the information is not available at the randomisation visit but at the (re)screening visit (Visit 1) then this will be used instead.

All the analyses specified in the protocol will be reviewed in relation to the blinded data actually obtained, and the statistical analysis plan will be finalised before breaking the randomisation code.

Any changes from the statistical analyses planned in this clinical trial protocol will be described and justified in a protocol amendment, the statistical analysis plan, and/or in the CTR, dependent on the type of change.

### 14.3.2 Handling of missing values

The methods for handling of missing values for the primary endpoint are described in Section 14.3.8.

THIS DOCUMENT CONTAINS CONFIDENTIAL INFORMATION AND MUST NOT BE COPIED OR MADE AVAILABLE TO ANY THIRD PARTY WITHOUT THE PRIOR WRITTEN CONSENT OF THE LEO PHARMA GROUP

For other continuous endpoints for which a MMRM analysis will be used it will be assumed that data is missing at random within each treatment group. The missing data will be predicted by the MMRM model.

For the categorical endpoints for which a CMH test will be used, subjects with missing data will be considered as non-responders and their missing values will be imputed using NRI.

### **14.3.3 Handling of intercurrent events related to the COVID-19 pandemic**

As the implications of the COVID-19 pandemic might, extraordinarily, influence trial events and data in manners not foreseen by the clinical trial protocol, this section introduces the statistical considerations for handling of intercurrent events related to the pandemic for the primary endpoint.

A supplementary estimand, ‘pandemic-modified composite’, is introduced for analysis of the primary endpoint to address permanent discontinuation of IMP due to the pandemic as an intercurrent event. Details are described in Section [14.3.8](#).

Interruption of IMP administration during the treatment period (Weeks 0–16) is not considered as an intercurrent event if only 1 full dose (450 mg) is missed. Observed data from subjects missing more than one dose will be ‘treated as missing’. The causal relationship of permanent discontinuation of IMP related to the pandemic will be recorded in the eCRF.

#### **Handling of data affected by the COVID-19 pandemic**

As a consequence of the pandemic and associated local preventive measures, subjects may miss an entire visit. At scheduled visits, it will be recorded in the eCRF whether data are missing due to the pandemic.

Observed data after permanent discontinuation of IMP related to the pandemic will be ‘treated as missing’ and imputed assuming MAR. Similarly, missing data and/or initiation of rescue treatment related to the pandemic will be imputed assuming MAR.

It should be noted that a subject may have missing data related to the pandemic, even though the subject has not experienced an intercurrent event related to the pandemic.

An overview of how observed and missing data will be handled according to the intercurrent events and their relatedness to the pandemic is presented in Section [14.3.7](#). For the primary analysis of estimands, details of the analysis are described in Section [14.3.8](#).

THIS DOCUMENT CONTAINS CONFIDENTIAL INFORMATION AND MUST NOT BE COPIED OR MADE AVAILABLE TO ANY THIRD PARTY WITHOUT THE PRIOR WRITTEN CONSENT OF THE LEO PHARMA GROUP

#### **14.3.4 Disposition of subjects**

The reasons for permanent discontinuation of IMP or withdrawal from trial will be presented for all randomised subjects by last visit attended and by treatment group.

A subject disposition summary table will be made including information of number of subjects who were screened, randomised, exposed and who completed the trial, permanently discontinued IMP, and/or were withdrawn from the trial (by treatment group and overall).

#### **14.3.5 Demographics and other baseline characteristics**

Descriptive statistics of demographics and other baseline characteristics will be presented for all randomised subjects and by treatment group. Presentations of date of birth, age, sex, ethnicity, race, and baseline EASI score by treatment group will be reported for all randomised subjects.

Other baseline characteristics include height, weight, BMI, duration of AD, concurrent diagnoses (from medical history and indications for concomitant medication), concomitant medication, and previous AD treatments.

#### **14.3.6 Exposure and treatment compliance**

Exposure to treatment will be presented for the safety analysis set as days of exposure per treatment group.

The cumulated dose administered to each subject will be determined and summarised descriptively. For subjects who withdraw from the trial, are lost to follow-up, or permanently discontinue IMP, their cumulated dose will be calculated up until the time of withdrawal/permanent discontinuation of IMP/loss to follow-up.

Treatment compliance will be presented for the safety analysis set per treatment group as the percentages of missed IMP doses.

#### **14.3.7 Testing strategy**

This is a phase 2a trial with the primary objective to investigate efficacy of LEO 138559. For the primary endpoint, change in EASI score from baseline to Week 16, the statistical analysis will be controlled by 2-sided alpha value of 5%. There will be no adjustment for the multiple testing of primary and secondary endpoints, all p-values will be considered nominal.

THIS DOCUMENT CONTAINS CONFIDENTIAL INFORMATION AND MUST NOT BE COPIED OR MADE AVAILABLE TO ANY THIRD PARTY WITHOUT THE PRIOR WRITTEN CONSENT OF THE LEO PHARMA GROUP

### 14.3.8 Analysis of primary endpoint

A primary and 3 supplementary estimands will be defined for the primary endpoint to ensure that occurrence of intercurrent events is taken into account ([Panel 12](#)).

THIS DOCUMENT CONTAINS CONFIDENTIAL INFORMATION AND MUST NOT BE COPIED OR MADE AVAILABLE TO ANY THIRD PARTY WITHOUT THE PRIOR WRITTEN CONSENT OF THE LEO PHARMA GROUP

## Panel 12: Objective and estimands for primary endpoint

Objective	Estimands					Endpoint
	Estimand type (Primary/Supplementary)	Comparison groups	Interpretation of endpoint	Intercurrent events and strategy	Population level summary	
Primary objective To compare the efficacy of LEO 138559 with placebo in subjects with moderate to severe AD.	Primary	Dose of LEO 138559 450 mg Q2W vs. placebo.	Change in EASI from baseline to Week 16 as if all subjects adhered to the treatment regimen, i.e., they did not permanently discontinue IMP and did not use rescue treatment before Week 16 (Section 14.3.8.1).	Events: Permanent discontinuation of IMP, initiation of rescue treatment Strategy: 'Hypothetical'.	Difference in mean change in EASI from baseline to Week 16.	Primary endpoint Change in EASI score from baseline to Week 16.
	First supplementary		Change in EASI from baseline to Week 16 without intercurrent events (Section 14.3.8.2).	Events: Permanent discontinuation of IMP, initiation of rescue treatment Strategy: 'Composite'.		
	Second supplementary		Change in EASI from baseline to Week 16 without intercurrent events and as if COVID-19 pandemic did not happen (Section 14.3.8.3).	Events: Permanent discontinuation of IMP due to non-pandemic-related factors, permanent discontinuation of IMP due to pandemic-related factors, initiation of rescue treatment Strategy: 'Pandemic-modified composite'.		
	Third supplementary		Change in EASI from baseline to Week 16 regardless of intercurrent events (Section 14.3.8.4).	Events: Permanent discontinuation of IMP, initiation of rescue treatment Strategy: 'Treatment policy'.		

**Abbreviations:** AD = atopic dermatitis; COVID-19 = coronavirus disease 2019; EASI = Eczema Area and Severity Index; IMP = investigational medicinal product; Q2W = every second week.

THIS DOCUMENT CONTAINS CONFIDENTIAL INFORMATION AND MUST NOT BE COPIED OR MADE AVAILABLE TO ANY THIRD PARTY WITHOUT THE PRIOR WRITTEN CONSENT OF THE LEO PHARMA GROUP

The following intercurrent events are considered to affect the interpretation of the estimated treatment effects:

- Initiation of rescue treatment: This event occurs when a subject initiates rescue treatment. This event is disallowed during the first 4 weeks of treatment but can occur from week 4 at the discretion of the investigator. The timing of the event will be taken as the date of initiation of the rescue treatment recorded in the eCRF and the event will be handled without assessing relatedness to the COVID-19 pandemic. If rescue treatment is initiated before week 4, the subject will be withdrawn from the trial.
- Permanent discontinuation of IMP independent of the COVID-19 pandemic: This event occurs when a subject permanently discontinues IMP independently of the pandemic. This event can occur at the subject's own initiative, at the discretion of the investigator or the sponsor, or if the subject is lost to follow-up. The timing of the event will be taken as the date of permanent discontinuation of IMP recorded in the eCRF.
- Permanent discontinuation of IMP due to the COVID-19 pandemic: This event occurs when a subject permanently discontinues IMP due to circumstances related to the pandemic; not attributed to lack of efficacy or randomised treatment features considered unacceptable by the subject.

Depending on the estimand strategy selected, the occurrence of an intercurrent event may be ignored, lead to the exclusion of data observed after the occurrence of the event, be accounted for in the definition of a composite endpoint, or restrict the relevant observation window to the time prior to the occurrence of the intercurrent event as described below.

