	Screening a)	Washout a)	Baseline/ Start of treatment	Treatment										End of treatment b) Primary endpoint c)	SFU phone calls	SFU site visit d)	Early IMP termination, if applicable e)	Unscheduled. Visit f)	References (Section in protocol)
Visit	1	2	3	4	5	6	7	8	9	10	11	12	13, 14, 15	16					
Week	-4	-1	0	1	2	4	6	8	10	12	14	16	20, 24, 28	32					
Day	-28	-7	1	8	15	29	43	57	71	85	99	113	141, 169, 197	225					
Visit window (days) g)	NA	NA	NA	±1	±3	±3	±3	±3	±3	±3	±3	±3	±3	±3					
Urine pregnancy test (females only) h)			X			X		X		X		X		X	(X)	(X)		11.4.5	
ADA			X			X		X		X		X		X	(X)	(X)		11.4.6	
Adverse events	X	X	X	X	X	X	X	X	X	X	X	X	X	X	X	X	X	13	
Pharmacokinetic assessment																			
PK blood samples			X	X	X	X	X	X	X	X	X	X		X	(X)	(X)		11.5	
Pharmacodynamic assessments																			
Blood biomarkers (PD serum sample)			X		X	X		X					X			(X)	(X)	11.6.2	
Skin swabs			X										X			(X)	(X)	11.6.3	
Tape strips			X										X			(X)	(X)	11.6.4	

THIS DOCUMENT CONTAINS CONFIDENTIAL INFORMATION AND MUST NOT BE COPIED OR MADE AVAILABLE TO ANY THIRD PARTY WITHOUT THE PRIOR WRITTEN CONSENT OF THE LEO PHARMA GROUP

	Screening a)	Washout a)	Baseline/ Start of treatment	Treatment												End of treatment b) Primary endpoint c)	SFU phone calls	SFU site visit d)	Early IMP termination, if applicable e)	Unscheduled. Visit f)	References (Section in protocol)
Visit	1	2	3	4	5	6	7	8	9	10	11	12	13, 14, 15	16							
Week	-4	-1	0	1	2	4	6	8	10	12	14	16	20, 24, 28	32							
Day	-28	-7	1	8	15	29	43	57	71	85	99	113	141, 169, 197	225							
Visit window (days) g)	NA	NA	NA	±1	±3	±3	±3	±3	±3	±3	±3	±3	±3	±3							
End of treatment/trial																					
End-of-treatment form													X			X			11.7		
End-of-trial form															X	X			11.7		

a) Screening will be performed up to 4 weeks before the baseline visit and can be combined with the washout visit (Visit 2) if needed.

b) An end-of-treatment form must be completed in the eCRF for all randomised subjects. See Section 11.7 for further details.

c) Subjects who permanently discontinue IMP treatment prior to Week 16 will be asked to return to the trial site at Week 16 for a primary endpoint (nominal Week 16) visit.

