## 9.5 Rescue treatment

If medically necessary (i.e., due to worsening of AD or intolerable AD symptoms), rescue treatment for AD in the form of TCS/TCI may be prescribed to trial subjects and used from Week 4 at the discretion of the investigator. It is recommended that the investigator starts with

THIS DOCUMENT CONTAINS CONFIDENTIAL INFORMATION AND MUST NOT BE COPIED OR MADE AVAILABLE TO ANY THIRD PARTY WITHOUT THE PRIOR WRITTEN CONSENT OF THE LEO PHARMA GROUP

a TCI or least potent TCS for the face (e.g., hydrocortisone 2.5% cream/ointment) and moderately potent TCS for the body (e.g., triamcinolone acetonide 0.1% cream/ointment).

If rescue treatment with TCS/TCI is initiated after Week 4, the subject will continue treatment and the schedule of trial visits and assessments. However, treatment with IMP will be discontinued if a subject receives the following treatment:

- Rescue treatment with any TCS/TCI before Week 4.
- Super potent TCS (e.g., clobetasol propionate 0.05% cream) between Week -1 and Week 16.
- Systemic rescue treatment (besides systemic antihistamines and/or anti-infectives) at any point during the trial between Week -4 (or from 5 half-lives of Week 0, whichever is longer) and Week 16.

Investigators should make every attempt to conduct efficacy and safety assessments (for example disease severity scores, safety labs) immediately before administering any rescue treatment. An unscheduled visit may be used for this purpose, if necessary.

During the safety follow-up period (Weeks 16 to 32), topical therapy (including TCS and TCI) may be prescribed to control disease activity at the discretion of the investigator and will not be considered as rescue treatment. Any medication taken by the subjects during the follow-up period will be reported as concomitant medication using the eCRF.

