## 10 Discontinuation and withdrawal

### 10.1 General principles

A subject may withdraw from the trial (prior to first dose or during the treatment period) or permanently discontinue trial treatment at any time if the subject, the investigator, or LEO Pharma considers that it is not in the subject's best interest to continue.

A subject who withdraws from the trial is a subject who stops treatment with the IMP and all further protocol defined trial activities. A subject who permanently discontinues IMP is a subject who, although they stop treatment with the IMP, agree to their follow-up as described in Section 10.3. Early termination assessments to be conducted for both events are described in Section 10.3.

Subjects who withdraw from the trial and subjects who permanently discontinue IMP will not be replaced.

If a subject withdraws from the trial, they may request destruction of any samples taken and not tested. The investigator must document this in the subject's medical record and inform LEO Pharma.

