### 10.2 Reasons for discontinuation of IMP

#### 10.2.1 Reasons for permanent discontinuation of IMP

Subjects will permanently discontinue IMP in the event of:

- Withdrawal of consent.
- An AE that, in the opinion of the investigator or sponsor's medical expert, contraindicates further dosing.
- Initiation of systemic rescue treatment of AD (besides systemic antihistamines and/or anti-infectives) at any point during the trial between Week 0 and 16, rescue treatment before Week 4, and/or super potent TCS between Week -1 and Week 16.
- Initiation of prohibited medication which cannot be safely replaced by other non-prohibited medications.
- Evidence of pregnancy, or if the subject is noncompliant with the contraception requirements (see Section 8).
- Other reasons, at the discretion of the investigator. If other, a specification should be provided.

THIS DOCUMENT CONTAINS CONFIDENTIAL INFORMATION AND MUST NOT BE COPIED OR MADE AVAILABLE TO ANY THIRD PARTY WITHOUT THE PRIOR WRITTEN CONSENT OF THE LEO PHARMA GROUP

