## 10.3 Early termination assessments

### Permanent discontinuation of IMP

Subjects who permanently discontinue IMP for any reason will be asked to attend an early termination visit as soon as possible after last administration of IMP and return to the trial site for additional visits as indicated below. See the schedule of trial procedures (Section 4) for data to be collected at these visits. Subjects who discontinue IMP but remain in the trial will continue completing the eDiary until the safety follow-up visit (Visit 16). The investigator will review any AEs which will be followed up according to Section 13.7, if the subject agrees.

Subjects who permanently discontinue IMP will be asked to attend:

THIS DOCUMENT CONTAINS CONFIDENTIAL INFORMATION AND MUST NOT BE COPIED OR MADE AVAILABLE TO ANY THIRD PARTY WITHOUT THE PRIOR WRITTEN CONSENT OF THE LEO PHARMA GROUP

- An early termination visit as soon as possible after last dose of IMP.
- The primary endpoint visit (16 weeks after randomisation).
- A safety follow-up visit (16 weeks after last administration of IMP).

Details on data to be recorded in the eCRF for subjects who permanently discontinue IMP can be found in Section 11.7.

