### **Withdrawal from trial**

Subjects who withdraw/are withdrawn from the trial prior to first dose of IMP (randomisation) will be considered screening failures.

Subjects who withdraw from the trial for any reason should attend an early termination visit as soon as possible after last administration of IMP. Assessments/procedures to be conducted at this visit are listed in the schedule of trial procedures (Section 4). If the subject agrees, the investigator will review any AEs which will be followed up according to Section 13.7.

Details on data to be recorded in the eCRF for subjects who withdraw from the trial can be found in Section 11.7.

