#### 14.3.8.4 Third supplementary estimand

A third supplementary estimand will use a *treatment policy strategy* which attempts to quantify the effect of the decision to treat subjects with the randomised treatment, thus ignoring the occurrence of intercurrent events. Data collected for the primary endpoint are used regardless of whether an intercurrent event (independent of the pandemic) occurred. Data collected after an event related to the pandemic will be 'treated as missing' and imputed assuming MAR.

This supplementary estimand will evaluate the treatment difference in change in EASI score from baseline to Week 16 regardless of permanent discontinuation of IMP or initiation of rescue treatment and as if the COVID-19 pandemic did not happen. Observed data will be used in the analysis, including the data observed after the occurrence of non-pandemic-related intercurrent events. For subjects who experience a pandemic-related intercurrent event prior to Week 16, observed data at Week 16 will be 'treated as missing' and imputed assuming MAR.

If data is missing at Week 16 due to a non-pandemic-related intercurrent event, the data will be imputed using MI (100 iterations) assuming MAR within each treatment group and whether the subject has experienced a non-pandemic-related intercurrent event. Within a given treatment group, observed data from subjects not experiencing an intercurrent event will be used to impute missing data for subjects who experience an intercurrent event.

Missing data or data 'treated as missing' at Week 16 due to the pandemic will be imputed using MI assuming MAR within treatment group using data from subjects who have not experienced an intercurrent event.

For each of the 100 complete datasets, the change in EASI score from baseline to Week 16 will be analysed using an ANCOVA model adjusted for treatment, region, baseline EASI

THIS DOCUMENT CONTAINS CONFIDENTIAL INFORMATION AND MUST NOT BE COPIED OR MADE AVAILABLE TO ANY THIRD PARTY WITHOUT THE PRIOR WRITTEN CONSENT OF THE LEO PHARMA GROUP

score, and baseline disease severity. The pooled estimate of the difference in the LS-mean change from baseline, along with the associated 95% CIs and nominal p-values will be presented based on applying Rubin's rules to the estimates and standard errors from the ANCOVA analysis of the imputed datasets.

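### Section 14.3.8 withdraws subjects rescued before Week 4 from the trial, while Sections 9.5, 10.2.1 and 10.3 only stop IMP and keep the Week 16 and safety visits

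*Combined protocol and SAP*

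**What the plan says.** Section 14.3.8, under initiation of rescue treatment, states: "If rescue treatment is initiated before week 4, the subject will be withdrawn from the trial".

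The operational sections say something else about the same event:

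- Section 9.5 introduces its list, which includes any TCS or TCI before Week 4, with "However, treatment with IMP will be discontinued if a subject receives the following treatment". It does not mention leaving the trial.
- Section 10.2.1 lists "rescue treatment before Week 4, and/or super potent TCS between Week -1 and Week 16" among the reasons for permanent discontinuation of IMP.
- Section 10.1 separates the two states: "A subject who withdraws from the trial is a subject who stops treatment with the IMP and all further protocol defined trial activities". By contrast, someone who stops IMP for good stays in follow-up under Section 10.3.
- Section 10.3 asks IMP discontinuers for an early termination visit, the Week 16 primary endpoint visit and a safety visit 16 weeks after the last dose. Footnote c of the schedule (Panel 2) repeats that they "will be asked to return to the trial site at Week 16 for a primary endpoint (nominal Week 16) visit".
- For withdrawals, Section 10.3 asks for one visit: "Subjects who withdraw from the trial for any reason should attend an early termination visit as soon as possible after last administration of IMP".

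On the analysis side, Section 14.3.8.4 says of the treatment-policy estimand: "Data collected for the primary endpoint are used regardless of whether an intercurrent event (independent of the pandemic) occurred". If the Week 16 value is missing, it is multiply imputed from subjects in the same arm who had no intercurrent event.

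**The concern.** A subject rescued before Week 4 is withdrawn under one section and kept in follow-up under the others. The protocol itself defines these as different states with different visits.

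Three things are at stake if Section 14.3.8 is followed.

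- **Treatment-policy estimand.** It is meant to reflect what happens after rescue or stopping IMP. Without a Week 16 visit, these subjects' values come from same-arm subjects who had neither event. For them, the analysis does what the primary hypothetical analysis already does.
- **Safety visit.** These subjects may have had up to three scheduled doses (Weeks 0, 1 and 2). The site visit that would collect ADA, laboratory and pregnancy tests 16 weeks after the last dose would not be scheduled.
- **Secondary endpoint.** It counts treatment-emergent adverse events to Week 16 per subject. Routine collection would stop early.

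**Working it through.** **Reading the two rules side by side**

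| | Sections 9.5, 10.2.1, 10.3 and footnote c | Section 14.3.8 |
|---|---|---|
| Status after rescue before Week 4 | IMP permanently discontinued | Withdrawn from the trial |
| Visits requested after last dose | 3 (early termination, Week 16, safety) | 1 (early termination) |
| Week 16 EASI | Sought | Not sought |
| Treatment-policy analysis (Panel 13) | Observed value used | Imputed, MI under MAR |

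The contradiction alone does not show which side is wrong. Two features of the current text do. First, Section 10.3 applies to anyone who stops IMP, whatever the reason. Second, where the protocol wants withdrawal as well as stopping IMP, it says so: a confirmed clinically significant ECG abnormality (Section 11.4.4) and pregnancy (Sections 11.4.5.2 and 13.5.1). Sections 9.5 and 10.2.1 add no such step for early rescue. As context only, the Amendment 2 history in Appendix 10 records that the withdrawal wording was taken out of Section 9.5 to align it with Section 10.1. The sentence in Section 14.3.8 looks like a leftover.

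**Which analyses are touched**

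- Primary (hypothetical): data after rescue or IMP discontinuation are set to missing and imputed. Not affected by the lost visit.
- First and second supplementary (composite): LOCF after these events. Not affected.
- Third supplementary (treatment policy): uses the observed value. Affected.

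**Planning figures (Section 14.1)**

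- Expected EASI reductions: 22.9 (SD 13) and 7.3 (SD 18); difference 22.9 − 7.3 = 15.6.
- Pooled SD = √((13² + 18²)/2) = 15.70.
- Two-sided 5% t-test with 18 per arm: power 0.825. The plan's figure of at least 80% reproduces.
- 18/(1 − 0.30) = 25.7, rounded up to 26 per arm, as stated.

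**Size of the effect (illustration)**

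The documents give no rate of rescue before Week 4. Assume k = 1 to 3 affected subjects in one arm of 26 (3.8% to 11.5%), each with an imputed value wrong by e = 5 to 10 EASI points in either direction.

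Shift in that arm's mean = k × e / 26:

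| k | e = 5 | e = 10 |
|---|---|---|
| 1 | 0.19 | 0.38 |
| 3 | 0.58 | 1.15 |

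Unadjusted standard error of the difference with 26 per arm = 15.70 × √(2/26) = 4.35.

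- Against the standard error: 0.19/4.35 = 0.04 to 1.15/4.35 = 0.27.
- Against the planned difference: 0.19/15.6 = 1.2% to 1.15/15.6 = 7.4%.

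**The case against.** The strongest reply is that this is a stray clause in a statistical definition. Sites work from Sections 9 and 10 and the schedule, which together lead to a Week 16 visit, and nothing suggests that a site would follow Section 14 instead. On efficacy, the harm reaches one supplementary estimand in a phase 2a trial whose p-values are all nominal. Even the correct rule only asks subjects to attend, so some Week 16 values would be missing anyway. The subject counts and the 5 to 10 point errors have no source in the documents.

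Much of this stands. The practical reach is small, the numbers are an illustration, and Sections 9.5 and 10.2.1 do not themselves mention the Week 16 visit, which comes from Section 10.3 and footnote c. Listing under Section 10.2.1 does not by itself rule out withdrawal either, since pregnancy is listed there and also leads to withdrawal.

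The objection does not remove the conflict. Withdrawal is a defined term here, and the rule as written gives the wrong handling for a defined group. A Week 16 assessment that was never sought cannot be recovered later.

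**Conclusion.** The concern holds. The sentence in Section 14.3.8 contradicts the current operational rules and should be corrected, but it does not threaten the trial's main result. Its effect on efficacy is confined to the treatment-policy estimand. Outside efficacy, it drops the scheduled safety visit and shortens adverse event collection for the secondary endpoint. The early termination visit and the follow-up of adverse events under Section 13.7 remain.

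Under the stated assumptions the affected arm's mean moves by 0.2 to 1.2 EASI points. The direction is unknown because the missing value would have been measured after rescue. The comparison with the standard error assumes the planning SDs and 26 analysed subjects per arm, with no covariate adjustment and no added imputation variance. The contradiction itself rests on no assumption.

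**What to change.** Replace the sentence in Section 14.3.8 with: *Subjects who start rescue before Week 4 stop IMP permanently and are followed under Section 10.3, including the Week 16 primary endpoint visit and the safety follow-up visit.*

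Carry the same rule into the SAP, which Section 14.3.1 says is finalised before the randomisation code is broken.

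The cost is one sentence in the protocol and the corresponding rule in the SAP. It adds no visits beyond those already in Section 10.3 and leaves the sample size unchanged.
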